The protocol, informed consent form(s), recruitment materials, and all participant materials will be submitted to the IRB for review and approval. Approval of both the protocol and the consent form must be obtained before any participant is enrolled. Any amendment to the protocol will require review and approval by the IRB before the changes are implemented to the study. All changes to the consent form will be IRB approved; a determination will be made regarding whether a new consent needs to be obtained from participants who provided consent, using a previously approved consent form.

1 PROTOCOL SUMMARY

1.1 SYNOPSIS

Title: Boost rTMS for AVH – Therapeutic Response and Neurobiological Prediction Markers in Auditory Verbal Hallucinations

Study Description: This is a randomized, placebo controlled, double-blind clinical trial. We aim to examine the efficacy of repeated transcranial magnetic stimulation (rTMS) for the treatment of auditory verbal hallucinations (AVH) in patients with schizophrenia who are not taking antipsychotic medication. We employ a novel, accelerated protocol with only 4 sessions of low-frequency rTMS in one day. The effects of this accelerated protocol will be compared to the sham stimulation. Additionally, we will examine the effects of rTMS on a neurophysiological level by evaluation mechanism of action in the temporo-parietal lobe.

Objectives: Primary Objective:
Examine the efficacy of low-frequency rTMS for AVH in patients with a schizophrenia spectrum disorder.

Secondary Objectives:
Examine the effects of rTMS on the quality of AVH, positive symptoms, general psychopathology, and the global level of functioning of these patients. Last, confirm that rTMS has no side effects on cognitive functioning.

Determine the neuroimaging-related biomarkers associated with response to rTMS using the baseline imaging parameters (rCBF, resting fMRI, T1, and DTI) to predict response to rTMS treatment. Further,

compare pre- and post-treatment imaging parameters (rCBF, resting fMRI, T1, and DTI) to characterize rTMS effects on AVH.

Endpoints:

Primary Endpoint:

- AVH assessed using the Hallucination Change Scale (HCS) at baseline (first visit), after the last TMS session, after the post-MRI.

Secondary Endpoints:

- a) Assessment of the qualitative content of hallucinations will be assessed using the revised Beliefs About Voices Questionnaire (BAVQ-R)
- b) Assessment of AVH as part of positive symptoms will be assessed with the Brief Psychiatric Rating Scale (BPRS)-subscale that includes "Hallucinatory Behavior", "Conceptual Disorganization", "Suspiciousness", and "Unusual Thought Content".
- c) Global functioning will be assessed using the Clinical Global Impression (CGI) and General Assessment of Functioning (GAF) questionnaires.
- d) Cognitive functioning will be assessed using the Repeatable Battery for the Assessment of Neuropsychological Status (rBANS).

Neurophysiological changes using magnetic resonance imaging (MRI) are investigated as predictors for rTMS treatment response.

Study Population:

N = 40

- Male and female subjects 18 to 65 years of age
- DSM V diagnosis of schizophrenia (295.90), schizoaffective disorder (295.70) or brief psychotic disorder (298.80) confirmed by SCID-V interview currently experiencing AVH in the acute phases of the disorder as assessed with the revised Beliefs About Voices Questionnaire (BAVQ-R).
- Patient agrees to rTMS for AVH treatment for 1 day before standard medication therapy.
- Right-handedness assessed with the Edinburgh Handedness Inventory
- Patient is competent to provide informed consent
- Inpatient at the Zucker Hillside Hospital
- No history of seizures

Phase:

N/A

**Description of
Sites/Facilities Enrolling
Participants:**

Participants will be recruited through the Zucker Hillside Hospital in-patient clinic. Recruitment will only take place at this site and no sites outside of the United States are included.

**Description of Study
Intervention:**

All patients receive 1Hz of rTMS over the Sylvian parietal temporal area (area Spt) four times on 1 day (1 pulse/second and a total of 1'000 pulses: 16 minutes' protocol at 100% of motor threshold modified based on

Hoffman et al. (1999)). Area Spt will be localized via baseline structural imaging and our Localite TMS navigation system.

Subjects will be withdrawn from the study if side effects become limiting, or if either the patient or principal investigator determine that rTMS should be discontinued.

[figure not shown]
Study Duration: 18 months in total including 12 months for recruitment and measurements plus 6 months for data analysis.

Participant Duration: Each participant is enrolled for up to 4 days of measurements (minimum of 3 days).

1.2 SCHEMA

Prior to
Enrollment
Visit 1

Total N = 40; Obtain informed consent; Screen potential participants by inclusion and exclusion criteria; obtain history.

Visit 2
Time Point

Baseline assessments

- Clinical interview which includes as the Hallucination Change Scale, the Believes About Voices Questionnaire, the Brief Psychotic Rating Scale, the Clinical Global Impression, the Global Assessment of Functioning, and the Repeatable Battery for the Assessment of Neuropsychological Status.
 - Blood sample to determine antipsychotic concentration.
 - Baseline MRI measurement.

Visit 3
Time Point

Study intervention

4 sessions of rTMS within 1 day.

Visit 4
Time Point

Final Assessments

- Clinical interview including the same questionnaires as the baseline assessment.
- Post-treatment MRI measurement.

1.3 SCHEDULE OF ACTIVITIES (SOA)

Visit	Screening	Enrollment/Baseline Assessment	Treatment Day	Follow-up Assessment
Procedures				
Informed consent	X			
Demographics	X			
Medical history	X			
Blood sample	X			
Randomization	X			
TMS screening questionnaire	X			
Administer study intervention			X	
Adverse event review and evaluation	X	X	X	X
Imaging assessment	X	X		X
Complete Case Report Forms (CRFs)	X	X	X	X

Note that the Screening Day is not specifically set. This day can either be on the first day of the study such that patients who are willing to participate could start immediately with the baseline measurements. While patients who are for example recruited in the evening would have their first day of the study on the following day. In the special case of enrollment on a Friday, the start of the study would be the following Monday. Thus, patients would have to declare that they do not want to take antipsychotics during the weekend and the time of the study. See section 2.3.1 "Known Potential Risks" for information.

Only for eligible patients for which an extra vial of blood was not collected for the measurement of serum level of antipsychotic, phlebotomy will be performed especially for this study in order to obtain the blood sample necessary to assess the serum antipsychotic concentration prior to the scanner.

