4 STUDY DESIGN

4.1 OVERALL DESIGN

This is a randomized, placebo controlled, double-blind clinical trial. We aim to assess the efficacy of rTMS as a potentially beneficial treatment option in drug-naïve patients and patients refusing antipsychotic medication who suffer from AVH. We use a novel protocol with only one day of treatment including 4 sessions of low-frequency rTMS and compare the effects with the sham stimulation. Further, we aim to examine structural and functional neurophysiological characteristics as predictors for rTMS.

As primary outcome, we aim to examine the efficacy of low-frequency rTMS for AVH in patients with a schizophrenia spectrum disorder with regard to AVH based on the HCS. Further, Hallucination quality (BAVQ-R), hallucinations as a part of positive symptoms (BPRS-subscale), clinical global improvement (CGI), and general assessment of functioning (GAF) are secondary outcome measures. Structural and functional neurophysiological characteristics (rCBF, resting fMRI, T1, and DTI) are investigated as potential predictors for rTMS treatment response.

In order to achieve these aims, we will have two intervention arms: real and sham rTMS. Patients who are willing to take part in the study and declining treatment by antipsychotic medication to sufficiently treat psychotic symptoms will be randomly assigned by the (trained) research coordinator to either sham or real rTMS.

Subjects will be randomized using a permutation block design to real rTMS or sham rTMS treatment. Accordingly, a well-documented double-blind randomization plan will be developed by the study's biostatistician and implemented in collaboration with the investigator. Copies of the resulting permutation blocks and randomization codes will be kept by the unblinded research coordinator. Blinded study personnel will not have access to these codes. When a new subject is randomized to a particular group, the research coordinator will provide written notice of the randomization condition of the subject to the operator of the rTMS.

Double-blinding is ensured by the fact that the trained research assistant who is performing the rTMS treatments is not the same person (rater) who will conduct the psychopathology assessments. This allows the unbiased assessment of changes in AVH severity due to rTMS without the prior knowledge of the rater whether the patient received real or sham rTMS.

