5.2 EXCLUSION CRITERIA

An individual who meets any of the following criteria will be excluded from participation in this study:

1. Therapeutic level of antipsychotic medication
2. ECT or rTMS within three months (see the TMS screening questionnaire)
3. History of seizures
4. Presence of implanted electronic device or metal implant in the head and neck region (DBS, cochlear implant, etc.)
5. Pregnancy, as assessed with a pregnancy test prior to every MRI measurement, or lactation
6. Any active general medical condition or CNS disease which can affect cognition or response to treatment
7. Treatment with another investigational drug or other intervention within 2 weeks
8. Current diagnosis of delirium, dementia, or amnestic amnesiac disorder; Diagnosis of mental retardation; Current (within the past three months) diagnosis of active substance dependence, or active substance abuse within the past week as indicated by self-report.
9. Patients who are cognitively impaired and are thus not able to give informed consent

Note, that other medication such as antidepressant, pain killers, or sleep medication are no exclusion criteria per se. Yet, if these medications are needed for the treatment of other mental illnesses such as subsumed under point 5 or 7 of the exclusion criteria then patients cannot be included in the study.

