receive the study intervention may be replaced. Subjects who sign the informed consent form, are randomized, receive the study intervention, subsequently withdraw or are withdrawn or discontinued from the study will be replaced.

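### The Schedule of Activities randomises at screening, before the baseline ratings, pregnancy test and baseline MRI, so losses in that window become replaceable post-randomisation exclusions

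*Combined protocol and SAP*

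**What the plan says.** The column headings in section 1.3 run "Visit Screening Enrollment/Baseline Assessment Treatment Day Follow-up Assessment", and the randomisation row has one mark, in the first of these columns: "Randomization X".

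The schema (1.2) lists only consent, screening and history at Visit 1. Visit 2 holds the baseline work: "Clinical interview which includes as the Hallucination Change Scale, the Believes About Voices Questionnaire, the Brief Psychotic Rating Scale" and the other scales, the baseline MRI, and "Blood sample to determine antipsychotic concentration". Section 5.2 excludes "Pregnancy, as assessed with a pregnancy test prior to every MRI measurement, or lactation". The compensation table in 5.5 shows no MRI on the Screening Day and the first one at baseline.

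On release of the arm, section 4.1 says: "When a new subject is randomized to a particular group, the research coordinator will provide written notice of the randomization condition of the subject"; the recipient is the rTMS operator.

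On losses, section 7.2 lets the investigator withdraw a patient for an exclusion criterion that was not recognised earlier. It adds that patients who consent and are randomised but do not "receive the study intervention may be replaced". Section 5.4 reserves the term screen failure for people who consent and are not then randomised. Section 9.3 analyses only patients who completed both MRI and interview visits and all four sessions.

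**The concern.** Randomisation protects the comparison of the patients who were allocated. Each allocated patient who is then removed and replaced weakens that protection. Here several ordinary reasons for not starting treatment can come to light only after the scheduled allocation: a positive pregnancy test, a contraindication or intolerance found at the MRI, an antipsychotic given on the ward, or a change of mind. The scan matters for treatment as well, because the stimulation site is located from it (6.1.2).

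Had these losses come before allocation, they would be screen failures with no bearing on the comparison. With allocation at screening, they are randomised patients who disappear from the analysis. At least two members of staff can also hold the allocation during a period in which withdrawal decisions and baseline data collection are still under way. Nothing before Visit 3 depends on the arm, so the early allocation gains nothing.

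**Working it through.** **The plan's own figure.** Section 9.2 assumes d = 0.9, 80% power and 5% alpha. The normal approximation, two-sided, gives n per arm = 2(1.960 + 0.842)²/0.9² = 2 × 7.85/0.81 = 19.4, so 20 per arm and 40 in total, as stated. The t-test gives 20.39 per arm, and power at 20 per arm is 79.2%. The point below is about the order of procedures and does not change N = 40.

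**Order of events, section by section.**

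- Randomisation: Screening column (1.3).
- Baseline HCS, BAVQ-R, BPRS, CGI, GAF and rBANS: Visit 2 (1.2).
- Baseline MRI: Visit 2 (1.2; compensation table in 5.5). Section 1.3 marks imaging under Screening as well as under baseline, which conflicts with both.
- Pregnancy test: before each of the two MRIs (2.2.1, 5.2, 8.3.9), hence at Visit 2 if the scan is there.
- Serum sample: Screening in 1.3, Visit 2 in 1.2, at hospitalisation or after consent in 4.2. The assay is done at an outside laboratory (6.2.1) and no turnaround time is given.
- Any rule that holds allocation until these are done: none in 4.1 or 6.3. Section 6.3 refers to 4.2 for further detail on randomisation, and 4.2 has none.

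**What happens to a patient lost between screening and session 1.** Not a screen failure (5.4 requires non-randomisation); may be replaced (7.2); outside the analysis set (9.3). Section 8.1 says that drop-outs and premature exits are analysed by carrying the last observation forward. Apart from its conflict with 9.3, that cannot help a patient lost before Visit 2, who has no HCS observation to carry forward.

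**Size, under assumed loss rates.** The documents give none. Number randomised to reach 40 = 40/(1 − loss), rounded up:

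- 5%: 40/0.95 = 42.1, so 43
- 10%: 40/0.90 = 44.4, so 45
- 20%: 40/0.80 = 50
- 30%: 40/0.70 = 57.1, so 58

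At 10% to 20%, 45 − 40 = 5 to 50 − 40 = 10 allocated patients would leave before treatment. Replacement of untreated patients is optional in 7.2. If it were not used, equal losses would leave 18 or 16 per arm, and power at d = 0.9 would be 74.6% or 69.3%.

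**The case against.** The strongest reply is that losses before session 1 cannot be caused by the treatment. With patient and rater blinded, they bias the comparison only if someone who knows the arm influences who is lost. That is largely right, and it limits the severity. It does not remove the exposure: 7.2 has the study coordinator monitor patients and judge non-compliance, and the documents do not say whether that person is the unblinded research coordinator of 4.1.

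A second reply is that screening and baseline may share a day (1.3) and that the screen-failure definition implies eligibility is checked first. Both shorten the window. Neither says that allocation waits for the ratings, the pregnancy test or the scan. Likewise, the imaging mark under Screening would, read literally, bring the pregnancy test forward, but 1.2 and 5.5 contradict it. Mock-scanner preparation and exclusion for significant claustrophobia (8.2) reduce MRI losses; 2.2.1 accepts that panic can occur in people with no such history.

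Three stronger readings are tempting and are not supported:

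- *The primary baseline is biased because staff know the arm.* The baseline HCS is set at 10 for everyone (section 3), and the rater is separate from the operator and does not know the arm (4.1, 6.3). Only the patient's narrative, against which later scores are judged, could vary. A constant baseline covariate could not correct for that, but no route from informed staff to the rater is described.
- *Patients are randomised before their serum result is known.* Specimens from non-consenters are never processed (4.2), and consent shares a column with randomisation, so this is plausible. But 1.3 draws blood at Screening, 5.5 places the blood levels with the confirmation of eligibility after consent, and no turnaround time is given. It is an inference.
- *Friday patients sit allocated for three days.* The note says "In the special case of enrollment on a Friday, the start of the study would be the following Monday", and in the table enrolment heads the baseline column. Nothing says that randomisation takes place on the Friday.

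**Conclusion.** The point holds as a sequencing fault that should be fixed. As scheduled, allocation precedes the baseline ratings, the pregnancy test and the baseline MRI, and no other section corrects this. Pre-treatment losses that could have been screen failures become post-randomisation exclusions, open to replacement and left out of the analysis, while the coordinator and operator can already know the arm.

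The size is unknown. The figure of 45 to 50 randomised to reach 40 rests wholly on an assumed loss of 10% to 20%. The order also depends on reading 1.3 together with 1.2, 2.2.1 and 5.5, because the table has no rows for the ratings or the pregnancy test. The risk is to comparability and transparency more than to sample size: replacement restores the count but not the randomised comparison. The documents do not establish that bias would occur.

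**What to change.** - In 1.3, move the randomisation mark from Screening to the Treatment Day, after the Visit 2 ratings, pregnancy test and baseline MRI are complete. State the same condition in 4.1 and 6.3.
- In 4.1, release the arm to the operator just before session 1.
- Count losses before that point as screen failures under 5.4, and limit the 7.2 replacement of randomised but untreated patients to losses after it.
- Resolve the imaging mark under Screening in 1.3 against 1.2 and 5.5.
- Reconcile 1.2, 1.3, 4.2 and 5.5 on when blood is taken and when the serum criterion is confirmed relative to randomisation. Because no laboratory turnaround is stated, requiring the result first could lengthen the time without antipsychotics. This point does not ask for a longer wait; the sponsor must settle the order.

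The cost of moving randomisation is one table cell and a few sentences, with no added visits or patients for that change. The code must be available on the treatment morning. The change does not cure the completers-only analysis or the replacement of treated patients who withdraw, which are separate matters.

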2 INTRODUCTION

2.1 STUDY RATIONALE

Schizophrenia is a disorder that affects communication, cognition, and emotion and thus leads to a high degree of suffering for patients (Sukhwinder S Shergill, Murray, & McGuire, 1998) and even to suicide attempts (Hor & Taylor, 2010). Up to 70% of schizophrenia patients suffer from auditory verbal hallucinations (AVH) (Waters, 2012), one of the cardinal symptoms of schizophrenia.

The most conventional therapeutic strategy is antipsychotic medication. Yet, in about 20-30% of patients even extended antipsychotic medication does not ameliorate AVH (Sukhwinder S Shergill et al.,

2007) and is often accompanied by side effects (Leucht et al., 2009). Therefore, it is crucial to develop and assess promising, potentially beneficial therapeutic options.

Non-invasive brain stimulation techniques like repetitive transcranial magnetic stimulation (rTMS) have been proposed to disrupt mechanisms in question. In particular, low-frequency (LF) rTMS is thought to decrease cortical excitability. In schizophrenia, Hoffman et al. (1999) were the first to introduce rTMS for the treatment of refractory AVH. The authors used LF rTMS (1Hz) over the left temporo-parietal junction (TPJ) and showed a significant reduction in AVH severity with effects lasting up to 15 weeks. Following this promising result, several studies replicated these findings (Brunelin et al., 2006; Chibbaro et al., 2005; Hoffman et al., 2000; Hoffman et al., 2005; Hoffman et al., 2007; Jandl et al., 2006; Klirova et al., 2013; Lee et al., 2005; Poulet et al., 2005; Vercammen et al., 2009), but others did not (Blumberger et al., 2012; de Jesus et al., 2011; Fitzgerald et al., 2005; Hoffman et al., 2013; Lee et al., 2005; Loo, Sainsbury, Mitchell, Hadzi-Pavlovic, & Sachdev, 2010; McIntosh et al., 2004; Rosa et al., 2007; Saba et al., 2006; Schönenfeldt-Lecuona et al., 2004; C. Slotema, Aleman, Daskalakis, & Sommer, 2012; C. W. Slotema et al., 2011).

This heterogeneity of results may be due to influencing factors such as rTMS protocols, parameters, and target regions. Nevertheless, a number of meta-analyses (Aleman, Sommer, & Kahn, 2007; Demeulemeester et al., 2012; Freitas, Fregni, & Pascual-Leone, 2009; C. W. Slotema, Blom, van Lutterveld, Hoek, & Sommer, 2014; C. W. Slotema, Dirk Blom, Hoek, & Sommer, 2010; Tranulis, Sepehry, Galinowski, & Stip, 2008) found significant effect sizes ranging from 0.42 to 1.04 for LF rTMS over the left TPJ. This indicates a medium to large effect for the treatment of AVH with rTMS. However, all studies so far investigated the effects of rTMS in treatment resistant schizophrenia patients as an ad-on or second-line treatment.

However, there are no studies to date that explored the effects of rTMS either as a first-line treatment or in the initial stage of the illness. This is surprising, considering the fact that rTMS is a safe treatment with minimal side-effects (Rossi, Hallett, Rossini, & Pascual-Leone, 2009) that could be used already in the earlier phase of treatment. Furthermore, another advantage of rTMS are the minimal side-effects associated with this treatment (Rossi et al., 2009). This stands in considerable contrast to the range of side-effects associated with antipsychotics (Leucht et al., 2017) that can be disabling leading to suffering for patients and lower quality of life. Therefore, it is crucial to develop new treatment options that in the future might provide alternatives to conventional therapy.

Noteworthy, previous studies in medicated patients focused mainly on treatment-resistant patients, which might be a special subgroup and not necessarily reflect the whole spectrum of schizophrenia patients including first episode patients who never had antipsychotic treatment. Therefore, investigating rTMS effects in patients from the whole schizophrenia spectrum are needed.

Further, the majority of studies used the standard protocol as described above that lasts for 10 consecutive days with one TMS session per day. Yet, daily administration of rTMS over the course of several days without antipsychotic medication could comprise risks, especially for patients suffering from additional psychotic symptoms. This may be one of the reasons that no study to date has investigated rTMS in patients with schizophrenia that did not take any antipsychotic medication.

Taken together, the crucial next step is (1) to explore the effects of rTMS in medication-free patients from the whole schizophrenia spectrum and (2) to use an accelerated protocol of multiple rTMS-sessions within a short period of time. To make this assessment feasible, considering that patients have to be off medication, the safest and also most efficient way is an accelerated rTMS protocol. The great advantage of such an approach is that the effects of rTMS can be investigated independently of potentially influencing effects of antipsychotics and at the same time assess the efficacy of rTMS within a very short amount of time.

In the proposed study, we aim to investigate the efficacy of rTMS as a potential treatment for AVH in schizophrenia besides an improved understanding of the neurobiology of schizophrenia and AVH and thus reduce suffering in patients and their relatives.

We will conduct a clinical trial in which we will collect neuroimaging data in patients undergoing one day of 4 sessions of LF rTMS. Imaging and neuropsychological data will be collected at baseline and at the end of the course of the treatment.

Background

Neuroimaging results in relation to AVH

Schizophrenia is a chronic psychiatric disorder associated with considerable morbidity and mortality (Dean, 2012). With a prevalence rate of 0.3 – 0.7 % of the population (van Os & Kapur, 2009), about 50 million people worldwide suffer from schizophrenia. Among these, up to 80% suffer from AVH (Linscott & Van Os, 2013), one of the most common symptoms of this disorder with diagnostic value. Due to their intrusive and often uncontrollable nature, AVH can be extremely emotionally distressing for patients and can lead to patients endangering themselves and others. Thus, an efficient therapeutic regimen is indispensable to lower suffering and costs. Unfortunately, therapeutic options are rather limited.

The most conventional therapeutic strategy is the use of antipsychotic medication, however, their efficacy is poor for many patients (Dean, 2012). In about 20 - 30 % even extended antipsychotic medication does not ameliorate AVH (Sukhwinder S Shergill et al., 1998). Also, many patients refuse medication or a necessary increase of the dosage even after exacerbation of symptoms. This may be due to the common side effects such as weight gain, somnolence, hyperprolactinemia, dystonia, and other movement disorders that, in some patients, require the dose or type of drug to be altered.

Beside conventional medicinal therapy, medication-free therapeutic regimens such as psychotherapy, psychoeducation, and psychosocial interventions offer some improvement with electroconvulsive treatment as a last resort. As a novel approach, non-invasive brain stimulation techniques such as transcranial magnetic stimulation (Hoffman et al., 1999; Hoffman et al., 2005; P Homan, Kindler, Hauf, Hubl, & Dierks, 2012; Philipp Homan et al., 2013; Jochen Kindler et al., 2013; J. Kindler et al., 2013; Kindler et al., 2012; C. W. Slotema et al., 2011) are being studied as options in the treatment of AVH with some promising findings.

Understanding the neuronal mechanisms underlying AVH, therefore, is of considerable scientific importance. First, structural alterations were found to be related to the severity of AVH: decreased gray matter (GM) volume in the left (Modinos et al., 2013) and right superior temporal gyrus (STG) and the left insula (Palaniyappan, Balain, Radua, & Liddle, 2012), decreased white matter (WM) integrity of the left arcuate fasciculus (Abdul-Rahman et al., 2012; Catani et al., 2011; De Weijer et al., 2011; Geoffroy et al., 2014; Daniela Hubl et al., 2004; McCarthy-Jones, Oestreich, Whitford, & Bank, 2015), as well as increased WM integrity in the arcuate fasciculus, the cingulum (Sukhwinder S Shergill et al., 2007), and the corpus callosum (D. Hubl et al., 2004; Mulert et al., 2012). Second, functional findings, e.g. summarized in the meta-analysis by Jardri et al.(2011), show a relationship between increased brain activity in fronto-temporal regions in the left hemisphere and in the hippocampal/parahippocampal gyrus and severity of AVH.

These results of structural and functional anomalies suggest that AVH arise from altered communication between brain regions and are not a result of localized alterations of single brain regions. This is in line with the idea of a fronto-temporal disconnection underlying AVH (Friston, 1998; Friston & Frith, 1995).

Brain stimulation using rTMS

Repetitive TMS uses a fluctuating magnetic field to induce a brief electrical current that generates an action potential propagating along neurons (Valero-Cabré, Payne, & Pascual-Leone, 2007; Valero-Cabré,

Payne, Rushmore, Lomber, & Pascual-Leone, 2005; Wagner, Valero-Cabré, & Pascual-Leone, 2007). In most studies, rTMS is applied over the course of several days causing short-term modulations of the target region and its connected network (Maeda, Keenan, Tormos, Topka, & Pascual-Leone, 2000; Valero-Cabré, Pascual-Leone, & Coubard, 2011). Low-frequency (LF) rTMS (1 pulse/second, 1 Hz) is thought to inhibit cortical excitability in the stimulated area. This effect depends not only on the stimulation frequency, but also on the time between pulses and other influencing factors (Lefaucheur et al., 2014).

In schizophrenia, Hoffman et al. (1999) were the first to introduce rTMS for the treatment of refractory AVH in treatment-resistant patients. The authors used LF rTMS over the left temporo-parietal junction (TPJ) and showed significantly reduced AVH severity with effects lasting up to 15 weeks. The TPJ is a sensory-motor integration area and is involved in the perception of speech (Benson et al., 2001; Fiez, Raichle, Balota, Tallal, & Petersen, 1996). The increased activity found in this region during AVH (S. S. Shergill, Bullmore, Simmons, Murray, & McGuire, 2000; Silbersweig et al., 1995) may arise from deficits in self-monitoring that, subsequently, lead to misinterpretation of inner speech (Frith, Friston, Liddle, & Frackowiak, 1992; Waters, 2012).

Since the first promising rTMS trials of Hoffman et al. (1999), many studies have used the classical LF stimulation pattern delivered to the left TPJ. Regarding this, meta-analyses (Aleman et al., 2007; Demeulemeester et al., 2012; Freitas et al., 2009; C. W. Slotema et al., 2014; C. W. Slotema et al., 2010; Tranulis et al., 2008) found significant effect sizes ranging from 0.42 to 1.04 which indicate a medium to large therapeutic effect of rTMS for the treatment of AVH.

However, most of the studies included patients with medication-resistant AVH. No study to date investigated rTMS in medication-naïve, high-risk individuals for psychosis or patients who are currently not taking antipsychotics who suffer from AVH in the relative absence of other severe positive or negative symptoms (C. W. Slotema et al., 2014). This is surprising, considering the fact that rTMS is a safe treatment with minimal side-effects (Rossi et al., 2009) that could be used already in the earlier phase of treatment. TMS could be applied as a first-line treatment for patients who primarily suffer from AVH, thus, exhaust other therapeutic options before turning to antipsychotics that are often associated with considerable side effects (Leucht et al., 2017) that impact on the patient's quality of life.

Furthermore, it is crucial to investigate the effects of brain stimulation independently of potentially influencing effects of antipsychotic medication. Teasing apart the effects of brain stimulation and antipsychotic drugs would allow a clearer assessment of the effects of brain stimulation and would help determine if brain stimulation techniques are useful as a first-line treatment or better implemented as an add-on to the conventional drug therapy. Yet, daily administration of rTMS over the course of several days without antipsychotic medication could comprise risks especially for patients suffering from further psychotic symptoms. Therefore, reducing the time of rTMS administration would, on the one hand, diminishes this risk and, on the other hand, reveals potentially beneficial effects of rTMS on AVH within a day, rather than two or more weeks typically needed with the classical rTMS protocol. Yet, no study to date has investigated rTMS for AVH in patients with schizophrenia who do not take antipsychotic medication. We aim to bridge this gap.

Following the above described line of thoughts, Holtzheimer et al. (2010) used an accelerated rTMS protocol of 15 sessions within 2 days in patients with treatment-resistant depression. Patients were stimulated with high-frequency rTMS in 5 sessions on the first day and 10 sessions on the second day. Being the first to use such an accelerated protocol in depression, Holtzheimer et al. (2010) showed promising results concerning safety and efficacy. This motivated further open-label studies investigating rTMS in depression, which found similarly promising results (McGirr, Van den Eynde, Tovar-Perdomo, Fleck, & Berlim, 2015; Tor, Gálvez, Goldstein, George, & Loo, 2016).

For AVH in schizophrenia, an accelerated protocol was used by Montagne-Larmurier et al. (2009) who administered two sessions of *high-frequency* rTMS (20Hz) on two days. Stimulation site was the posterior part of the left superior temporal sulcus that corresponds to the target area Spt proposed in this

study. The results were remarkable: Severity of AVH was significantly reduced ($p < .01$) with an effect size of 1.26 after the two day TMS treatment, lasting for 5.9 days ($SD = 6.75$). Notably, rTMS was well tolerated in all patients (no seizures) with headache as a side effect in only two cases. This study showing promising results of the accelerated protocol regarding safety and efficacy provides further evidence of the feasibility to shorten and thus accelerate rTMS protocols without loss of efficacy.

Yet, the majority of brain stimulation studies in schizophrenia-related AVH used *low-frequency* rTMS, but no study to date investigated the efficacy and safety of an accelerated low-frequency protocol. Low-frequency rTMS has the advantage of lower risk of side effects such as seizures than high-frequency rTMS (Rossi et al., 2009). Based on this and considering that in depression even 5 up to 10 sessions of high-frequency rTMS were applied, we expect that the application of 4 sessions of low-frequency rTMS will not impact on tolerability, safety or increased side-effects.

Based on this, we aim to assess the safety and efficacy of open-label accelerated rTMS, delivered over one day with four sessions, in first-episode schizophrenia patients who suffer from AVH and who decline first-line treatment with antipsychotic medication. We aim to further investigate the predictive value of cerebral blood flow, following the promising results of Homan et al. (2012), in first-episode schizophrenia patients.

In this project, we propose a translational approach to take the basic knowledge about the neurobiological underpinnings of AVH into direct clinical use, in a study of therapeutic outcome and related neurobiological changes and predictors of AVH.

